11.2 Secondary Endpoints

Secondary endpoints of the study will include (1) local control, (2) overall survival, (3) need for surgical re-excision due to inadequate margin, (4) Soft tissue fibrosis of the breast, (5) Breast pain, (6) radiologic and pathologic response, and (7) cosmetic outcome. The re-excision rate and rate of partial/complete response will be estimated with exact confidence intervals, and compared to historical controls (28 and 95) using Chi-Square or Fisher's exact tests. Kaplan-Meier survival estimates or estimate of the cumulative incidence rate will be used where censoring or competing risks occur (local control, cosmetic outcomes, fibrosis, and pain).

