2.2 Secondary

- 2.2.1 Measure rates of breast fibrosis and pain for patients treated with APBI and compare with historical controls of patients treated with post-operative APBI.
- 2.2.2 Collect data on cosmetic outcomes for patients treated with pre-operative APBI
- 2.2.4 Measure rates of need for re-excision because of a close or positive margin after pre-operative APBI.
- 2.2.5 Record long term outcomes of local recurrence rates and overall survival of patients treated with this modality.
- 2.2.6 Demonstrate the feasibility of MRI-based treatment planning for pre-operative APBI and compare dosimetric data from treatment planning with patients treated on a previous institutional post-op APBI protocol.
- 2.2.7 Study changes in MRI imaging from pre-treatment evaluation, treatment planning, and pre-surgical imaging and correlate those changes to pathological response.
- 2.2.8 Measure changes in tumor gene expression and immune response to radiation therapy and correlate this with pathologic response.

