3.1.9 Patient must provide study specific informed consent prior to study entry

- 3.1.10 Prior breast augmentation, including breast implants, is allowed
- 3.1.11 Patients with a prior history of contralateral breast cancer will be considered eligible if they completed all treatment (including anti-endocrine therapy) more than 2 years prior to registration
- 3.1.12 Patients must not have a prior treatment of malignancy diagnosed or treated within the past two years, with the exception of non-melanomatous skin cancer, carcinoma in situ of the cervix and contralateral breast cancer as described in 3.1.11.
- 3.1.13 Interested patients must meet with a medical oncologist prior to study entry to determine if a genomic profiling tests (such as Oncotype or MammaPrint) is recommended. If recommended and patient is amenable to the possibility of receiving chemotherapy, there must be adequate biopsy tissue for testing. If adequate tissue is not available for the testing, patients who are very interested in participation may undergo additional biopsies. If a patient plans to refuse chemotherapy regardless of a high profiling results and elects to forgo the test, they will still be eligible for enrollment.

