10.2 Cosmetic Outcomes

- 10.2.1 Physician reported cosmetic outcome has been consistently reported from prospective studies evaluating new methods for breast radiation. It is important to document physician reported cosmetic outcomes with this novel treatment method as well.
- 10.2.2 Physician assessed cosmetic outcome will be assessed prior to radiation, at the end of radiation, one month following radiation prior to surgery, one month after the last surgery, six months after surgery, 12 months after surgery and then annually until 5 years after treatment is completed.
- 10.2.3 Cosmetic assessments will be assessed using a 4 point scale. The form contained in Appendix III will be used for data collection.
- 10.2.4 Digital photographs will be taken of the treated and untreated breasts using an RTOG established protocol familiar to the research associates at Froedtert Hospital. These images will be taken prior to treatment, one month after surgery, then 6 months, 12 months, 24 months and 36 months after surgery. Two digital images will be taken at each of these assessment points. One will be a close up of the treated breast alone in order to provide detailed information regarding the treatment effects. The second digital image will be a straight frontal view of both breasts taken in either a standing or seated position with the patient's hands symmetrically placed on her hips. Care will be taken to exclude the face and framing and focusing will be done to include both the treated and untreated breast to allow optimal comparison for symmetry.
- 10.2.5 Photos will then be saved in MCW's secure I: drive with the following naming convention:

Save photo as: "Case #, View, Time Point" (ex. 7 Single_6mo; or 12 Both_1)

Breast View: Single = Treated breast; Both = Both breasts

Time Point: B=Baseline prior to radiation; 1mo = 1 month post-surgery; 6mo = 6months post-surgery; 1 = 1 year post-surgery; 2 = 2 years post- surgery; 3 = 3 years post-surgery

- 10.2.6 The digital images will later be evaluated for cosmetic results by the investigators using the criteria established in previous trials (again see Appendix III). It is of interest and important to obtain multiple measures of cosmetic outcome. With this protocol, three methods will be undertaken – physician reported outcomes assessed at time of follow-up, photographs to be evaluated by the investigators, and patient reported outcomes as described in the next section.

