APPENDIX 1 – Patient Assessments

Screening

Assessments	Within 90 Days of Enrollment	Within 60 Days of Enrollment
History and Physical, Performance Status and Height and Weight Documentation		X
Biopsy Proven Invasive Breast Cancer	X	
Breast Examination		X
Bilateral Mammogram		X (within 60 days of diagnosis)
Clip placed in tumor, verified by mammogram		X
CBC w/diff and ANC		X
Complete Metabolic Panel		X
Determination of hormone receptor and her2 status	Prior to enrollment	
Ultrasound or MRI of axilla with biopsy of any enlarged/abnormal lymph nodes		X (within 42 days of enrollment)
Consultation with Medical Oncologist	Prior to enrollment	
If Oncotype or Mammaprint is recommended, assessment of adequacy of biopsy specimen	Prior to enrollment	

Assessments During Treatment

Assessments	Prior to Start of RT	Last Day of RT (+/- 1 treatment)
History and Physical or weekly review, Performance Status and Weight Documentation	X	X
Breast Examination	X	X
Adverse event evaluation		X
Physician Cosmetic and QOL Questionnaire	X	X
Breast Photos	X	
Specimens for Research (blood, biopsy specimen)	X	X (blood only)*

*Optional for those treated outside Froedtert Hospital

Follow-up Assessments

Assessments	4-6 weeks After RT Completion	Within 4-6 weeks after Last Surgery	6 Months (+/-2wks) After Surgery	12 Months (+/- 1 month) After Surgery then Annually* (+/- 2 months)
History and Physical, Performance Status and Weight Documentation	X	X	X	X (until year 5)
Breast Examination	X	X	X	X (until year 5)
Adverse event evaluation	X	X	X	X (until year 5)
Specimens for Research (Blood, surgical specimen)	X (Blood)	X (surgical specimen)		
Physician Cosmetic and QOL Questionnaire	X	X	X	X (until year 5)
Breast Photos		X	X	X (until year 3)
Breast MRI	X			
Mammogram of Ipsilateral Breast			X	
Mammogram of Bilateral Breasts* (based on surgical date)				X (until year 5)**

*Follow-up and mammogram interval of every 12 months +/- 2months will be calculated from the actual date of the previous follow-up visit or mammogram.

**The mammogram to be done 12 months (+/- 1 month) after surgery is optional based on standard of care mammography schedules.

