Participants should complete this questionnaire at baseline (after consent and prior to randomization) and at end of radiation therapy, one month after radiation therapy (prior to surgery), one month after surgery, 6 months post-surgery, 12, 24, 36, 48, and 60 months after surgery or chemotherapy whichever is later. The first page is to be completed by a clinical staff member. Fill in the items listed on this page, print the patient's study ID at the top of pages 2 through 7 and give the questionnaire to the patient for completion. After the patient has completed the questionnaire, verify that the date has been recorded at the top of page 2, and submit the completed questionnaire to the CRA/CRC in the Clinical Trials Office.

Please administer the questionnaire at an office visit if possible. If that is not possible, mail the questionnaire to the patient, then call to ask for the patient's responses over the phone.

Staff Member Administering Form

Last Name

First Name

Phone

Time point for this questionnaire – Circle One

Baseline (after consent, prior to radiation)	2 years after surgery
Last Day of radiation therapy	3 years after surgery
4 weeks (1 month) after the end of radiation therapy (prior to surgery)	4 years after surgery
1 month post-surgery	5 years after surgery
6 months post-surgery	
12 months after surgery (whichever is later)	

This form is being filled out: (Mark one.)

- | | |
|---|--|
|  By participant in doctor's office |  By clinical staff, on phone with participant |
|  By participant not in doctor's office |  Other |

Record the participant's study ID on each of the remaining pages before giving the questionnaire to the participant.

Date this questionnaire is completed:
Month Day Year

(For example, if you were completing the questionnaire on September 8, 2014, you would write 09 08 2014 in the boxes.)

Thank you for completing this questionnaire.

We are interested in your evaluation of your physical appearance and functioning since you have been treated for breast cancer. Please rate the following items on this four-point scale, according to your evaluation at this point in time.

	Difference between treated and untreated breast and area			
	None	Slight	Moderate	Large
1 Breast size.....	1	2	3	4
2 Breast texture (hardening).....	1	2	3	4
3 Arm heaviness.....	1	2	3	4
4 Nipple appearance.....	1	2	3	4
5 Shoulder movement.....	1	2	3	4

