Before any treatment to your breast, the size of your breasts was: (Select the phrase that best describes your breast size prior to treatment.)

Larger
on left

The same on
both sides

Larger
on right

The size of your breasts now is: (Select the phrase that best describes your breast size now.)

Larger
on left

The same on
both sides

Larger
on right

Thank you for completing this questionnaire!

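### Pre-radiation pain, fibrosis and cosmesis are collected but not used in the analysis, and adverse events are not graded before radiation, so pre-existing findings may be counted as treatment effects

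*Combined protocol and SAP*

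**What the plan says.** Section 11.2 lists soft tissue fibrosis, breast pain and cosmetic outcome as secondary endpoints. Its method is one clause: Kaplan-Meier or cumulative incidence estimates "will be used where censoring or competing risks occur (local control, cosmetic outcomes, fibrosis, and pain"). No event, threshold, instrument or use of a baseline value is given. Objective 2.2.1 is to "Measure rates of breast fibrosis and pain for patients treated with APBI and compare with historical controls of patients treated with post-operative APBI". Section 10.3.6 likewise proposes comparing the BCTOS data with historical controls and does not mention within-patient change.

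Baseline values are collected. Section 10.2.2 states: "Physician assessed cosmetic outcome will be assessed prior to radiation, at the end of radiation". On photographs, section 10.2.4 states: "These images will be taken prior to treatment, one month after surgery". The physician form in Appendix III has a pre-treatment time point and a fibrosis item scored 0 to 2. The patient questionnaire, which contains BCTOS and four 0-10 pain ratings, is completed before treatment (section 10.3.4), and section 4.1.1 requires pre-treatment forms and photographs.

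CTCAE grading is different. Section 10.1.5 places it at follow-up visits. In Appendix 1 the row "Adverse event evaluation" is absent from the screening table, is empty in the column before the start of radiation, and is marked for the first time on the last day of radiation. History, physical and breast examination are marked at the pre-radiation visit.

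**The concern.** Time-to-first-event methods assume that every patient is free of the event at time zero. That may not hold here. All patients have had a core biopsy and clip placement (sections 3.1.3 and 3.1.5). Some may have had further biopsies (3.1.13) or have implants (3.1.10), and section 3.1.11 adds: "Patients with a prior history of contralateral breast cancer will be considered eligible if they completed all treatment" more than two years earlier. BCTOS scores the "Difference between treated and untreated breast and area", so asymmetry that predates the trial scores above the lowest category. A woman whose opposite breast was treated may have no untreated side to compare with. The questionnaire itself acknowledges pre-existing asymmetry with an item beginning "Before any treatment to your breast, the size of your breasts was".

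At stake are the rates in objective 2.2.1 and the reading of the cosmetic data. Sections 1.1, 1.2 and 1.7 argue that irradiating less breast tissue should reduce fibrosis and late toxicity and improve cosmesis. In a single arm of 40, no concurrent control absorbs whatever was present at baseline.

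**Working it through.** The plan states no rate, power or baseline prevalence for these endpoints, so there is no figure to reproduce. The check has two parts.

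**What is collected and what is used**

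| Source | Value before radiation? | Use stated in the analysis |
|---|---|---|
| Physician cosmetic form, including fibrosis item | Yes (10.2.2, Appendix III) | None |
| Photographs | Yes (10.2.4) | None as a baseline |
| BCTOS and 0-10 pain items | Yes (10.3.4) | Historical comparison of BCTOS only (10.3.6) |
| CTCAE grade | Not scheduled (10.1.5, Appendix 1) | Source for 11.2 not stated |

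Elsewhere the protocol does fix a baseline. Section 4.2.4 takes MRI baseline measurements from the simulation scan, and section 9.2.4 compares gene expression before and after radiation. No equivalent sentence exists for pain, fibrosis or cosmesis.

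**What the omission could do to a rate**

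Let b be the share of patients with the condition before radiation, t the new-onset rate among those free of it, and w the share of baseline-positive patients who worsen. All three are assumed. Three readings of section 11.2 are open:

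- Any occurrence counts: rate = b + (1 - b)t. The excess over t is b(1 - t). This takes every baseline condition as still recorded later.
- Baseline-positive patients are excluded: rate = t, in 40(1 - b) patients.
- New or worse counts: rate = (1 - b)t + bw, which equals t if w = t.

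Any-occurrence rates:

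| b | t = 5% | t = 10% | t = 20% | Extra events in 40 at t = 10% |
|---|---|---|---|---|
| 0% | 5% | 10% | 20% | 0 |
| 5% | 9.8% | 14.5% | 24% | 1.8 |
| 10% | 14.5% | 19% | 28% | 3.6 |
| 20% | 24% | 28% | 36% | 7.2 |
| 30% | 33.5% | 37% | 44% | 10.8 |

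Example: b = 10%, t = 10% gives 0.10 + 0.90 × 0.10 = 0.19. The excess is 0.10 × 0.90 = 0.09, and 40 × 0.09 = 3.6 events.

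The choice of reading matters. At b = 20% and t = 10%, the first gives 28% (40 × 0.28 = 11.2 expected events). The second gives 10% of 32 patients (3.2 events). The third gives 10% if w = 10%, or 0.80 × 0.10 = 8% if no baseline-positive patient worsens. The plan does not choose among them.

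**The case against.** The strongest reply is that section 11.2 is silent rather than wrong. A reader might infer that it counts any fibrosis, pain or poor cosmesis as an event. It does not say so, and a sensible analyst could use the baseline without breaching the plan. That stands, so the defensible statement is that pre-existing findings may be counted. The silence still leaves the choice until the data are visible.

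A reader might also infer that the trial has no baseline at all. That is true only of scheduled CTCAE grading. The forms give pre-radiation pain, fibrosis and cosmesis, and nothing names CTCAE as the source for these endpoints. The cosmetic scales also allow comparison with the breast's original appearance, which partly protects cosmesis. The protection is incomplete because the rater may use the opposite breast instead. BCTOS has no such alternative.

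A third inference is that the comparison is biased against the trial's own hypothesis. That cannot be established. It depends on how the historical series handled baseline findings, which the documents do not report. If those series also give absolute rates, baseline prevalence may sit on both sides.

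The illustration also assumes that baseline conditions persist. If biopsy soreness resolves before follow-up, the excess shrinks. Finally, objective 2.2.2 asks only that cosmetic data be collected, so for cosmesis the issue is interpretation, not a planned test.

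**Conclusion.** The point holds for secondary endpoints. Section 11.2 leaves available baseline values unused, and following Appendix 1 as written loses the pre-treatment CTCAE grade, which cannot be obtained reliably once radiation has begun. With assumed baseline prevalence of 5% to 30% and true new onset of 10%, an any-occurrence rate would read 14.5% to 37%, or 1.8 to 10.8 additional events in 40 patients. The bias is zero if prevalence is zero, or if prevalent cases are excluded or counted only when worse at the same rate t. Neither prevalence nor the direction against historical controls can be established from the documents. The primary endpoint, complications within three months of surgery, is unaffected, as is the two-stage design built on it.

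**What to change.** 1. In Appendix 1, mark adverse event evaluation in the column before the start of radiation, at the visit where history, physical and breast examination are already done.
2. In section 11.2, name the instrument for each endpoint. Count fibrosis and pain only when new or worse than the patient's own pre-radiation value on that instrument. Analyse BCTOS and the 0-10 pain items as change from baseline.
3. Report cosmesis with the pre-radiation category shown, for example change to fair or poor among patients rated excellent or good before radiation. Treating any one-category drop as an event is not advised, because excellent to good is only a slight difference on the Appendix III scale.
4. For patients with a treated opposite breast, use change from their own baseline scores. Photographs alone would not serve: they cannot show pain or texture, and they stop at 36 months while physician scoring runs to five years.
5. Keep absolute rates alongside for the historical comparison.

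The cost is one table cell, a few minutes of grading at an existing visit, a short paragraph in section 11.2 and a little extra analysis. One limit remains: lumpectomy falls between baseline and late follow-up, so change from baseline combines the effects of radiation and surgery.

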- 10.3 Quality of Life Outcomes and Patient Reported Outcomes
- 10.3.1 The Breast Cancer Treatment Outcome Scale (BCTOS) is a 22 item measure of perceived aesthetic (e.g. breast shape) and functional status (e.g. pain and mobility) that has been used after breast conserving therapy and radiation (Appendix IV)
- 10.3.2 The BCTOS has high reliability and validity and has been used in a variety of previous studies on recovery from breast cancer treatment, including studies of post-operative APBI.
- 10.3.3 The BCTOS focuses on symptoms that are specifically relevant to radiation therapy (e.g. skin problems, breast tenderness, fibrosis)
- 10.3.4 These forms will be completed prior to treatment, at the end of treatment, one month after radiation, one month after surgery, then 6 months after surgery, then 12 months, 24 months, 36 months, 48 months and 60 months after surgery or chemotherapy (if given), whichever is later. These may be collected +/- 2 months from the specified time points.
- 10.3.5 The BCTOS will ideally be completed at clinic visits, but may be completed by mail or over the phone by research associates.
- 10.3.6 As the BCTOS has been used on previous studies of radiation therapy, the data collected from this study can then be compared to historical controls of patients treated with more traditional post-operative radiation therapy regimens including post-operative APBI.
- 10.4 Patient Safety Monitoring and Confidentiality
- 10.4.1 This study will be reviewed by the Medical College of Wisconsin Cancer Center Data and Safety Monitoring Committee (MCWCC DSMC). A summary of the MCWCC DSMC activities are as follows:
- 10.4.1.1 Review the clinical trial for data integrity and safety
 - 10.4.1.2 Review all unexpected grade 3, and all grade 4, and 5 adverse events, as well as any others requiring expedited reporting as defined in this protocol. (Grades 4 & 5 events must be reported to the DSMC within 5 calendar days of study staff's knowledge.)
 - 10.4.1.3 Review all Data and Safety Monitoring reports.
 - 10.4.1.4 Submit a summary of any recommendations related to study content.
 - 10.4.1.5 Terminate the study if deemed unsafe for patients.
- 10.4.2 A copy of the MCWCC Data and Safety Monitoring Plan and membership roster will be maintained in the study research file and updated as membership changes. The committee will review reports from the study PI twice annually (or more

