These questions are about how you feel and how things have been with you during the past 4 weeks. For each question, please give the one answer that comes closest to the way you have been feeling.

How much of the time during the past 4 weeks...

	All of the time	Most of the time	Some of the time	A little of the time	None of the time
--	-----------------------	------------------------	------------------------	----------------------------	------------------------

1. Did you feel full of life? 1 2 3 4 5
2. Did you have a lot of energy? 1 2 3 4 5
3. Did you feel worn out? 1 2 3 4 5
4. Did you feel tired? 1 2 3 4 5

5. Rate your pain at its worst in the past four weeks. (Circle one number.)

0	1	2	3	4	5	6	7	8	9	10
---	---	---	---	---	---	---	---	---	---	----

No pain

Pain as bad as you
can imagine

6. Rate your pain at its least in the past four weeks. (Circle one number.)

0	1	2	3	4	5	6	7	8	9	10
---	---	---	---	---	---	---	---	---	---	----

No pain

Pain as bad as you
can imagine

7. Rate your pain on average in the past four weeks. (Circle one number.)

0	1	2	3	4	5	6	7	8	9	10
---	---	---	---	---	---	---	---	---	---	----

No pain

Pain as bad as you
can imagine

8. Rate how much pain you have right now. (Circle one number.)

0	1	2	3	4	5	6	7	8	9	10
---	---	---	---	---	---	---	---	---	---	----

No pain

Pain as bad as you
can imagine

9. Are you currently receiving treatments or taking medications for your pain?

Circle one: Yes No

--	--

By circling one (1) number per line, please indicate how much you have been bothered by each of the following problems **in the past four weeks.**

	Not bothered at all	A little bit bothered	Some- what bothered	Bothered quite a bit	Bothered very much
Fever or shivering (shaking, chills).....	0	1	2	3	4
Swelling of breast (breast feels larger).....	0	1	2	3	4
Breast heaviness.....	0	1	2	3	4
Breast warm to touch.....	0	1	2	3	4
Breast skin is red.....	0	1	2	3	4
Breast skin is tanned.....	0	1	2	3	4
Breast skin or area around nipple is pale in color.....	0	1	2	3	4
Breast skin is flaking or peeling.....	0	1	2	3	4
Bleeding or fluid leakage from breast.....	0	1	2	3	4
Breast itching.....	0	1	2	3	4
Blisters on the breast (or breast skin moist and raw).....	0	1	2	3	4
Coughing.....	0	1	2	3	4
Difficulty breathing.....	0	1	2	3	4
Muscle aches.....	0	1	2	3	4
Rib or chest wall pain.....	0	1	2	3	4
Infections.....	0	1	2	3	4
Slow healing of breast wounds.....	0	1	2	3	4
Visible small blood vessels (spider veins).....	0	1	2	3	4

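### Section 11.2 names only first-occurrence estimators for pain and cosmesis, which are current-state scores repeated over five years, so the planned analysis cannot show recovery or the proportion affected at a given visit

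*Combined protocol and SAP*

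**What the plan says.** Section 11.2 lists local control, soft tissue fibrosis, breast pain and cosmetic outcome among the secondary endpoints. Exact confidence intervals and chi-square or Fisher tests are given to re-excision and response only. For the others, Kaplan-Meier or cumulative incidence estimates "will be used where censoring or competing risks occur (local control, cosmetic outcomes, fibrosis, and pain"). The section defines no event for pain, cosmesis or fibrosis: no threshold, time point, rule for patients already affected at baseline, or rule for recovery.

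The measurements are described elsewhere:

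- **Cosmesis.** Section 10.2.3: "Cosmetic assessments will be assessed using a 4 point scale". Section 10.2.2 schedules it before radiation, at the end of radiation, one month after radiation, and then "one month after the last surgery, six months after surgery, 12 months after surgery and then annually until 5 years after treatment is completed".
- **Pain.** The quality-of-life questionnaire has a breast pain item in the 22-item scale, answered for the present time, and 0 to 10 items such as "Rate your pain on average in the past four weeks". Section 10.3.4 schedules it before treatment, at the end of treatment, one month after radiation, one and six months after surgery, "then 12 months, 24 months, 36 months, 48 months and 60 months after surgery or chemotherapy (if given), whichever is later".
- **Fibrosis.** The physician form in Appendix III scores it 0, 1 or 2 at each visit. Section 10.1.5 also grades toxicity by CTCAE at follow-up.

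Objective 2.2.1 is to "Measure rates of breast fibrosis and pain for patients treated with APBI and compare with historical controls of patients treated with post-operative APBI". Objective 2.2.2 asks only that cosmetic data be collected.

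**The concern.** Local recurrence fits a time-to-event analysis. A pain score for the past four weeks, or a cosmetic rating of the breast as it looks now, is a state that may be present at one visit and absent at the next. Both methods in section 11.2 take the first occurrence and hold the patient as an event from then on.

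The trial's rationale (sections 1.1 and 1.2) is less late toxicity and better cosmesis, so the useful question is how many women are affected at, say, three or five years. A curve that mixes pain one month after surgery with lasting pain does not answer it. The protocol itself expects some early pain: section 10.1.4 counts a need for pain medication because of seroma among the post-operative complications. The baseline scores, which would show how many women were affected before any treatment, have no role in section 11.2.

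The comparison in objective 2.2.1 is also exposed. An ever-affected proportion built from seven visits is comparable with a control figure only if that figure is of the same type and comes from a similar schedule. Section 11.2 secures neither.

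**Working it through.** The plan gives no figure for these endpoints, so there is none to reproduce. The check compares what a first-occurrence curve estimates with the proportion affected at the visit.

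**Inputs from the documents.** Seven post-operative assessments: 1, 6, 12, 24, 36, 48 and 60 months (sections 10.2.2 and 10.3.4). The 36-month visit is the fifth and the 60-month visit the seventh.

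**Assumed inputs.** The documents give no onset, persistence or prevalence for these outcomes. All values of q, s, p and rho below are assumptions. Dropout and death are left out.

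**Model 1: onset and persistence.** Patients start unaffected. Let q be the chance that an unaffected patient is affected at the next visit, and s the chance that an affected patient is still affected at the next visit.

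- Ever affected by visit k: 1 − (1 − q)^k
- Affected at visit k: P_k = P_(k−1)·s + (1 − P_(k−1))·q, with P_0 = 0

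Example with q = 10% and s = 0.5. Ever affected by visit 5 = 1 − 0.9^5 = 41.0%. Affected at visits 1 to 5 = 10.0%, 14.0%, 15.6%, 16.2%, 16.5%. Ratio 41.0/16.5 = 2.5.

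Results at 36 months (percent affected at the visit, with the ratio ever/current in brackets):

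| q | Ever | s = 0 | s = 0.5 | s = 0.8 | s = 1 |
|---|---|---|---|---|---|
| 5% | 22.6 | 4.8 (4.7) | 8.9 (2.5) | 15.3 (1.5) | 22.6 (1.0) |
| 10% | 41.0 | 9.1 (4.5) | 16.5 (2.5) | 27.7 (1.5) | 41.0 (1.0) |
| 15% | 55.6 | 13.0 (4.3) | 23.0 (2.4) | 37.9 (1.5) | 55.6 (1.0) |

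The gap widens with further visits. At 60 months with q = 10%, ever affected is 52.2%, against 9.1%, 16.6% and 30.6% for s = 0, 0.5 and 0.8: ratios 5.7, 3.1 and 1.7.

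**Model 2: constant prevalence p with within-patient correlation.** Each patient has a latent normal score with correlation rho between any two visits and is affected when it exceeds t = Φ⁻¹(1 − p). With Z standard normal,

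P(ever in 7 visits) = 1 − E[(1 − Φ((√rho·Z − t)/√(1 − rho)))^7].

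By numerical integration:

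| p | rho 0.5 | rho 0.8 | rho 0.9 | rho 0.95 | rho 0.99 |
|---|---|---|---|---|---|
| 10% | 34.5% (3.5) | 23.5% (2.3) | 18.9% (1.9) | 16.0% (1.6) | 12.5% (1.25) |
| 20% | 55.1% (2.8) | 40.0% (2.0) | 33.5% (1.7) | 29.2% (1.5) | 23.9% (1.2) |

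**Reading.** The first-occurrence figure is never below the visit figure, because everyone affected at a visit has by then been affected at least once. How far above it lies depends on persistence: nothing at s = 1, and from about 1.2 (Model 2, rho 0.99) to 4.7 (Model 1 at 36 months, s = 0) elsewhere. That range describes these assumptions and is not a bound, as the 60-month figures show.

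**The case against.** Much can be said for the plan.

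*Fibrosis.* A reader might infer that all three outcomes are reversible. The documents do not say so. Section 1.1 ties fibrosis risk to irradiated volume, and section 1.2 groups adverse cosmesis with late toxicity. The form lets a later fibrosis score return to 0, but that is only a scoring option. If fibrosis persists, the two measures coincide, and cumulative incidence of first fibrosis at a stated grade is a legitimate target. This objection stands, and fibrosis is left out of the main criticism.

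*Deaths.* A reader might infer that deaths will simply be censored. The same sentence offers cumulative incidence for competing risks; what it omits is which method goes with which endpoint. Section 3.2.18 excludes patients with a life expectancy of 10 years or less, so deaths should be few.

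*Historical controls.* A reader might infer that the comparison in objective 2.2.1 is bound to be invalid. That would require knowing what kind of rate the controls report, which the documents do not state. If a control reports ever-occurrence, a visit proportion would create the mismatch. Objective 2.2.1 also does not cover cosmesis. Section 10.3.6 leaves room for other comparisons of the patient-reported scale, though it gives no method.

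*Event rules.* The plan does not state that pain at one month counts as failure. It defines no event at all, so the most that can be said is that the named methods allow this and nothing in section 11.2 prevents it.

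*Dropout.* Time-to-event methods handle losses over five years; simple visit proportions do not. This also stands and is carried into the fix.

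None of this answers the narrow point: for pain and cosmesis the only estimators named are first-occurrence estimators, and the instruments record current state.

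**Conclusion.** The point holds for pain and cosmesis. Followed as written, section 11.2 yields a rising curve that cannot show recovery, can carry an early post-surgical score forward as permanent, gives the baseline score no role, and lies at or above the proportion affected at any given visit.

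Only the direction is firm. The size runs from no gap under full persistence to roughly 1.2- to 4.7-fold under the assumed ranges. A reader might take a fixed multiplier, such as a two- to three-fold overstatement, from the middle of the tables; the documents give no onset, prevalence or persistence to support one.

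The point does not extend to fibrosis and does not show that the historical comparison fails. It shows that the comparison is undefined until the type of rate is matched. These are secondary endpoints with no decision rule attached, and the primary complication test is unaffected. The change is worth making because it is cheap and lets data already scheduled answer the late-effects question.

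**What to change.** Amend section 11.2 as follows.

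1. **Pain and cosmesis.** Name the instrument and state the threshold for each. Report the proportion at or above it among patients assessed at named visits, for example 12, 36 and 60 months, with exact confidence intervals. Show the baseline proportion and the number missing at each visit alongside. State the clock for the questionnaire visits, since section 10.3.4 counts the 12- to 60-month ones from surgery or chemotherapy, whichever is later.
2. **Repeated-measures model.** Optional. With about 39 patients the data are thin: 4 affected of 39 has an exact 95% interval of 2.9% to 24.2%.
3. **Local control.** Keep cumulative incidence, with death as a competing risk.
4. **Fibrosis.** If wanted, keep cumulative incidence of first fibrosis at or above a stated grade, labelled as ever-occurrence.
5. **Objective 2.2.1.** Compare with each historical control using the type of rate that the control reports, ever or at a fixed time.

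The cost is analysis text only; the assessments are already scheduled. The downside is that visit proportions use only the patients assessed at that visit, so selective dropout can bias them. That is why the number missing must be shown.
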